We found evidence for the effectiveness of PiPT in the carrier study as well. Subjects in the intervention arm reported learning coping strategies that are associated with good outcomes. Responses to the question "Please list the most important things you learned in physical therapy?" differed between the two groups. Among subjects on the intervention carrier, 33.7% indicated they had learned concepts consistent with PiPT treatment based on a priori analysis criteria developed by the investigators. For example, one intervention subject said, "Stress and physical pain have a connection". In contrast, none of the subjects from the control carrier responded in this manner. Our experience with PiPT training has informed the development of the present proposal.

In our interdisciplinary training for the RCT described above, we avoided some of the weaknesses highlighted in previous studies by giving specific examples of how to implement guideline-based care for each discipline and by providing weekly teleconferences to answer questions, discuss difficult cases and reinforce training. In addition, we encouraged the use of self-care techniques to reduce patient reliance on health care professionals. This further distinguished our approach from Overmeer's. In our training for US Navy PT staff aboard a carrier we replicated our original training while incorporating important aspects found to be effective in other studies, such as ongoing role-playing and case-examples once the PT staff was deployed through teleconference.

The long-term objective of our research is to implement PiPT in different settings and for different cohorts of patients with MSD, throughout the Military. Therefore, we propose a full-scale study replicating the design and methods used in our pilot carrier study to test the feasibility and short- and long-term effectiveness of PiPT on psychological and functional outcomes in ADSM seeking care for MSD at a shore based rehabilitation setting; Navy Medical

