
t e d e

a y P e ;6

st, C n 11

r F S t 31

o o V q

p ll a u

hio rie

zi w a st

n - blio

g U e n

p s

1

,

2

,

3

B

a

s

e

li

n 0

e D -

F S e 6

e u p s

a r e c

r v n al

ofe d e

my F e ;6

o , A n 12

v B t 52

e o Q V q

mll a u

e o rie

n w a st

t - blio

U e n

p s

1

,

2

,

3

B  
a  
s  
e  
li  
n 4  
e Dp  
S et  
u ps  
r ec  
D v nal  
is e de  
tr y A n 6  
e ' D t 4  
s S Vq  
s o ll a u  
o rie  
w a st  
- blio  
U en  
p s  
1

,

2

,

3

A

ff 5

e p

O Bct t  
r aiv Li  
g s e C k  
g e co e  
c li o n e  
o n mfo rt  
m e mu ; 8  
m S it n 4 0  
it u md q  
m r e e u  
e v n r e  
n v n r st  
t et io  
t y s n  
c n  
al s  
e

5

p

J B t  
o a Li  
b s C k  
s e o e  
o li n rt  
cin D fo; 8  
cin R u 1 4  
s S R n 2 4  
u u d q  
p r e u  
p v r e  
o e st  
rty io

n

s

1

-

5

B s  
a c  
s C  
e o

li P n al  
n Cfoe 7  
eL u ; 7  
S- n 1  
uMd 7  
r eq  
v ru  
e e  
y st  
io  
n  
s  
0  
-

B 3  
a s  
Ds Cc  
e e o al  
p li Cn e  
r nE fo; 7  
e eSu 2 4  
s S- n 0  
siuDd q  
o r e u  
n v r e  
e st  
y io  
n  
s  
0

B -  
a 3  
s C s  
e o al  
A li Gn e  
n nA fo; 7  
xieDu ; 7 6  
e S- n  
tyu 7 d q  
r e e  
v r st  
e io  
y n  
s

B  
a  
s  
e  
li  
n  
e  
M S  
e u  
n r C  
t v h o Y  
al e h n Y  
H r fo e n  
e e e s n  
al' e u / /  
t F n a  
t o d N  
h ll e o  
C o m r  
a w  
r -  
e u  
p  
1  
,

,  
3  
B  
J a  
o s C  
b e Sio 1  
s l i n n -  
a n g l f o 5 7  
t i e e u s 9  
s f S i t n c  
a u e d a l  
c t r m e e  
i o v r  
n e

y  
B  
a  
W s C  
o e Sio 1  
r l i n n -  
k n g l f o 5 n  
s t e e u s /  
r S i t n c a  
e u e d a l  
s r m e e  
s v r  
e  
y

F  
u l  
B I  
a D  
s u  
e t  
l i y  
n ;  
e Li  
S m  
u it  
Dr e  
u v Sio d  
t y e n n D  
S y g l f o t n  
t , e u y /  
a F i t n a  
t o e d ;  
u l l m e M  
s o r e  
w d  
- B  
u o  
p a  
1 r  
, ;  
2 O  
, t  
3 h  
e  
r

P  
e  
rc D  
e i B e F  
v a p r  
e s e e  
d e S i n e  
b l i n d R  
a n g l e R  
r r e e n e

ieSItt s 1  
rsue V p 1  
r ma o  
t v rin  
o e as  
c y ble  
a e  
r  
e

Follow-up Questionnaire Batteries

- Post 4th treatment session- 77 items long, including one open field question
- 6 and 12mo – 68 items (excludes MRPS scale and outcome expectation)

C  
o V  
II a R C  
A e rie i  
R c ass i  
T ti b p t  
I O l o a  
A O l o t  
B L en i  
P T s o  
L o y e n  
E i p s n  
n e  

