## 11.6 Data Analysis Plan: Complete description: Background, Objectives, Design, Step by Step how the project is going to be done, Data analysis plan:

In order to assess for significant differences between two cohorts of patients, bivariate comparisons will first be conducted using a Chi-squared (Fisher exact) test to compare proportions of categorical (dichotomous outcomes) and an unpaired t-test for mean changes of continuous outcomes (i.e. Pain Disability Index scale, self-efficacy, positive outcome expectation, catastrophizing, fear avoidance beliefs and distress).

Alternatively, Wilcoxon nonparametric counterpart will be used for continuous variables where there is deviation from normality. These univariate analyses will be followed by multivariable regression methods for an adjustment of all other potential confounding variables. We will also use longitudinal logistic models (i.e., mixed-effects regression models with a random subject effect and GEE with exchangeable and independent correlations) to analyze the changes of the outcome at baseline at all follow-up times (baseline, post-treatment, at 6 months, and 1 year). Psychological outcomes will be analyzed at baseline and at post-treatment (approximately 4 weeks of enrollment). The models will be specified with random intercepts and slopes such that a linear trajectory representing outcomes will be compared between two arms. For example, longitudinal changes in all available continuous psychological outcomes over time of follow-up will be displayed using locally weighted smoothing scatter (lowess) plots, identifying nonparametric mean trajectories over time. Mean trajectories then will be modeled with mixed-effects linear regression models, and if necessary using segment-linear models to approximate non-linear mean trajectories for ease of interpretation. Group (arm)-specific (as well as individual-level) intercepts and slopes over the period of follow-up will be included as random effects, while other covariates such as other clinical or demographic confounders will be modeled as fixed effects. An interaction term will be also assessed to test group differences in outcomes over time. Residual-based diagnostics will be used to evaluate validity of model assumptions. Two sided p-values <0.05 will be considered to be statistically significant. All statistical procedures will be performed using R statistical package ([www.R-project.org](http://www.R-project.org)).

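### Section 11.6 contradicts itself on whether psychological outcomes are analysed to about 4 weeks or through 12 months

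*Combined protocol and SAP*

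**What the plan says.** Four statements in Section 11.6 bear on the time horizon, in this order:

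1. Longitudinal models are planned for an outcome that is not named, "at all follow-up times (baseline, post-treatment, at 6 months, and 1 year").
2. The next sentence reads: "Psychological outcomes will be analyzed at baseline and at post-treatment (approximately 4 weeks of enrollment").
3. The sentence after that gives the model form: "The models will be specified with random intercepts and slopes such that a linear trajectory representing outcomes will be compared between two arms".
4. An example follows: "longitudinal changes in all available continuous psychological outcomes over time of follow-up will be displayed using locally weighted smoothing scatter (lowess) plots". The mean trajectories are then to be fitted with mixed-effects linear models, in segments if they are not linear, with an interaction term for group differences over time.

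Elsewhere, Section 9.2 proposes a full-scale study of "short- and long-term effectiveness of PiPT on psychological and functional outcomes". Section 9.3 and Aim 3 name psychological follow-up measures but give no time point. Section 10.1 places the follow-ups after the 4th PT visit and at 6 and 12 months. The variable tables in Section 10.2 list PSEQ, PCS, FABQ and HADS at baseline and at follow-ups 1, 2 and 3. The later batteries are described as "6 and 12mo – 68 items (excludes MRPS scale and outcome expectation").

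**The concern.** Statement 2 is the only one in Section 11.6 that attaches named time points to the psychological outcomes, and it stops at about 4 weeks. Statement 4 carries the same outcomes over follow-up but names no time point. Two analysts could each defend their reading, one reporting 4-week results and the other 12-month results, and the horizon could be settled after the data have been seen.

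At stake is whether any change in catastrophizing, fear avoidance, self-efficacy or distress lasts. The first follow-up cannot show that. It comes after the 4th visit, while Section 10.1 gives an average of 6 visits, so a patient with the average number would still have two to come. The sample size reasoning also sits badly with a 4-week horizon: Section 11.5 asks for 200 participants per cohort who complete all follow-up, and Section 11.6 applies the power calculation to each outcome domain.

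**Working it through.** **The plan's own figures.** Items in the first follow-up battery, read from the Section 10.2 tables: injury location 1, pain intensity 1, outcome expectation 1, quality of life 1, PDI 7, PSEQ 10, PCS 13, FABQ 15, HADS 14, mental health care 3, MRPS 8, outcome satisfaction 1, duty status 1, lessons learned 1.

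- Sum: 1+1+1+1+7+10+13+15+14+3+8+1+1+1 = 77, the stated length.
- Without MRPS and outcome expectation: 77 − 8 − 1 = 68, the stated length at 6 and 12 months.

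The tables are broken in the text available, and the 3 items for mental health care are a reading of one such table. That both totals reproduce supports the reading.

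**Share of the later batteries that depends on the answer.** PSEQ 10 + PCS 13 + FABQ 15 + HADS 14 = 52 items, and 52/68 = 76% at each of months 6 and 12. This is two of the three post-baseline assessments of these scales. Outcome expectation is not affected, because it is collected only at baseline and follow-up 1. CES-D, GAD-7 and PCL-M are not affected either: they are listed at baseline only, as confounders.

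**Whether the stated model fits two time points.** Take y = (b0 + b1·t) + e, with intercept variance s00, slope variance s11, their covariance s01 and residual variance se. That is four parameters. For a baseline value y0 and one later value yt:

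- Var(y0) = s00 + se
- Cov(y0, yt) = s00 + s01·t
- Var(yt) = s00 + 2·s01·t + s11·t² + se

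If t is the same for everyone, or is coded as visit number, there are 2·3/2 = 3 distinct moments for 4 parameters, and the model is not identified.

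If t is elapsed time and differs between patients, two distinct values of t are enough. The two covariances give s00 and s01, Var(y0) then gives se, and Var(yt) gives s11. The information on the slope variance may be weak. The plan ties this visit to the 4th session and calls it approximately 4 weeks, so t may vary. The plan does not say how time will be coded.

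With all four assessments at common times there are 4·5/2 = 10 moments for 4 parameters, and the model is identified.

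**Effect on power.** There is none. Table 2 gives 84.9% for a standardized difference of 0.3 with 286 per cohort and 30% loss. With 286 × 0.70 ≈ 200 per cohort and two-sided 0.05, the t-test power is 84.9%, as stated. The point concerns which assessments are analysed and changes no sample size.

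**The case against.** The strongest reply is that long-term psychological analysis is already planned. The restricting sentence does not contain the word only. The sentence before it covers baseline to 1 year, and the later example says that "longitudinal changes in all available continuous psychological outcomes over time of follow-up will be displayed" and that the trajectories will then be modelled with a group-by-time interaction. The sentence on random intercepts and slopes can be taken to refer to the four-time-point models introduced first, where identification is not a problem. The restricting sentence may simply be loose drafting.

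Most of this stands, and it rules out three stronger inferences that a reader might draw.

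- That the plan has decided to drop long-term psychological analysis. The documents point both ways within one section, so this is a contradiction and not a settled omission.
- That 76% of the later questionnaire will go unused. That figure holds only if the restricting sentence is the one followed.
- That the random-slope model cannot be fitted. That needs two time points, and common or visit-coded times as well.

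It is also fair that the long-term wording comes from Section 9.2. Section 9.3 and Aim 3 set no horizon, and what Section 9.2 calls the long-term objective of the research is implementation across settings and cohorts, not durability of effect.

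The reply does not remove the contradiction. The neighbouring sentences leave either the outcome or the time points unnamed, and the one sentence that names both points to about 4 weeks.

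**Conclusion.** The point holds as an internal contradiction in Section 11.6 that should be resolved. Its size depends on which text is followed. Under the restricting sentence, the 6- and 12-month data on four scales (52 of 68 items at each assessment) stay out of the cohort comparison, the long-term psychological part of the Section 9.2 proposal goes unanswered, and the random-slope model is unidentified or at best weakly identified for these outcomes. Under the neighbouring sentences, the data are used and the model is identified.

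The item share assumes that the broken tables have been read correctly. The identification result assumes an unrestricted random intercept and slope with a common residual variance. No stated power or sample size figure is called into question.

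**What to change.** Replace the restricting sentence in Section 11.6 with wording such as:

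> PCS, FABQ, PSEQ and HADS will be analysed at baseline, after the 4th session, at 6 months and at 12 months. Outcome expectation will be analysed at baseline and after the 4th session only, without a random slope.

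Add that the between-cohort difference will be reported from the longitudinal model at the 4th session (short term) and at 12 months (long term). Treating time as a category is one way to obtain these two differences. It is an option and not a required part of the change, since the plan already allows segmented trajectories.

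The cost is a sentence or two. The data are already scheduled, so enrolment, participant burden and stated power do not change. The wording should be settled before outcomes are compared between cohorts.

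### The longitudinal mixed model lists the two-level study arm among the random effects and leaves the arm-by-time term undefined; arm, time and arm-by-time should be fixed, with random effects for participant only

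*Combined protocol and SAP*

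**What the plan says.** The point concerns one model in Section 11.6: the mixed model with random intercepts and slopes.

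- **Arm terms.** "Group (arm)-specific (as well as individual-level) intercepts and slopes over the period of follow-up will be included as random effects". The same sentence assigns the other clinical and demographic covariates to the fixed part. Section 11.4 defines two arms, pre-training and post-training.
- **Group test.** "An interaction term will be also assessed to test group differences in outcomes over time". Nothing says whether this term is fixed or random, and no estimation method is named.
- **Time shape.** "The models will be specified with random intercepts and slopes such that a linear trajectory representing outcomes will be compared between two arms". A fallback is allowed: "Mean trajectories then will be modeled with mixed-effects linear regression models, and if necessary using segment-linear models". No knot and no trigger are given. The plan also has "locally weighted smoothing scatter (lowess) plots, identifying nonparametric mean trajectories over time" and states: "Residual-based diagnostics will be used to evaluate validity of model assumptions".
- **Timing of the effect.** The footnote on the 4th visit in Section 10.1 says the investigators expect the groups to differ by then.
- **Visits for psychological outcomes.** One sentence reads "Psychological outcomes will be analyzed at baseline and at post-treatment (approximately 4 weeks of enrollment". A later sentence in the same section displays and models these outcomes over the whole follow-up.
- **Other analyses.** Section 11.6 also plans unpaired t-tests of mean change, adjusted regression, and "mixed-effects regression models with a random subject effect and GEE with exchangeable and independent correlations". None of these is said to treat arm as random.

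**The concern.** A variance estimated from two levels rests on a single contrast, and that contrast is the treatment comparison itself. Treating arm as random therefore either competes with the fixed effect for the same information or replaces a test of a difference with a test of a variance. Section 9.2 aims at short- and long-term effectiveness, and this is the model in which the arms' trajectories are compared. If the text is followed literally, the reported p-value can depend on the software default (ML or REML, starting values) rather than on the data. Section 11.6 also plans to combine results over multiply imputed data sets, so an arbitrary standard error would pass into the combined result.

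A smaller issue lies in the time shape. A slope difference over a year asks whether the arms keep diverging. The footnote in Section 10.1 expects a difference early, and such a difference could then hold, fade or grow.

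**Working it through.** **Inputs from the documents.** Two-sided alpha 0.05 (Section 11.6); 200 completers per arm and standardized effect 0.3 (Section 11.5); visits at baseline, post-treatment (about 4 weeks), 6 and 12 months (Section 11.6).

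**Assumptions.** Times 0, 1, 6 and 12 months; total variance 1; within-person correlation 0.5 (range 0.3-0.7); no participant slope variance. Effect shapes are assumed, because the documents give none.

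**1. The plan's own figure.** A t-test with 200 per arm and effect 0.3 has noncentral-t power 84.9%, which matches Table 2. The enrolment figure in that row also follows: 200/0.7 = 286.

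**2. Ordinary slope test (arm fixed).** Mean time is 4.75 and the sum of squared deviations is 90.75. The slope variance per arm is A = 0.5/(200 × 90.75) = 2.755e-5, so SE(difference) = √(2A) = 0.0074. A sustained effect (0, 0.3, 0.3, 0.3) gives slope 0.3 × 4.75/90.75 = 0.0157, z = 2.12 and power 56% (43-78% over the correlation range).

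**3. Interaction fixed, random arm slope (SD τ) kept.** SE = √(2(A + τ²)); the estimate does not change. The last column is the rise in -2 log-likelihood under ML, 2 ln(1 + τ²/A).

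| τ per month | z | p | REML log-likelihood | ML rise |
|---|---|---|---|---|
| 0 | 2.12 | 0.03 | same | 0 |
| 0.005 | 1.53 | 0.13 | same | 1.29 |
| 0.01 | 0.98 | 0.33 | same | 3.07 |
| 0.02 | 0.54 | 0.59 | same | 5.48 |

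REML cannot choose among these rows; ML chooses τ = 0. A trial fit on simulated data with 40 per arm agrees: the REML standard error was 1.07 against 0.018 for the standard model, while the ML standard error was 0.0177 with the arm variance at essentially zero.

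**4. Arm slopes only random.** With w = z², the REML likelihood-ratio statistic is w - 1 - ln(w) for w > 1, and 0 otherwise.

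- Cut-off 3.84 (chi-square, 1 df) requires |z| > 2.598: true size 0.009, power 31%.
- Cut-off 2.71 (50:50 mixture) requires |z| > 2.322: true size 0.020, power 42%.
- The fixed slope test has 56%. With the arm-intercept variance also free (20,000 simulations), sizes are 0.008 and 0.018, and power is 38% and 49%.

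**5. Straight line against effect shape.** The 4th-visit change contrast has SE √(2/200) = 0.1, z = 3.0 and power 85% (72-97% over the correlation range). Power of the slope test:

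| Difference at 4th visit / 6 / 12 months | Time in months | Time as visit number |
|---|---|---|
| 0.3 / 0.3 / 0.3 | 56% | 81% |
| 0.3 / 0.2 / 0.1 | 6% | 10% |
| 0.3 / 0.4 / 0.5 | 99% | above 99% |

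For the sustained shape, a segment-linear model with its knot at the 4th visit recovers 0.30 SD there, with 88.5% power. With the knot at 6 months it shows a change of only 0.03 SD by the 4th visit.

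**6. Two visits only.** A line through two times is exact, so step 5 falls away. A correlated random intercept and slope plus residual has 4 covariance parameters where a 2×2 covariance supports 3. If intercept and slope are uncorrelated, it is 3 for 3.

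**The case against.** The best defence is that the sentence is loosely worded and means arm-specific mean lines with participant random effects. The plan speaks of mean trajectories compared between arms, an interaction term and two-sided p-values, all of which suit a fixed contrast better than a variance test. That is a fair reading of the intent. But the sentence names the arm-level terms as random alongside the individual-level ones and sets them against fixed covariates, so the text does not settle it.

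A reader might infer that no reading which keeps the random arm effects gives a sound test. That is too strong. Under ML the ordinary test returns, although only because the arm variance goes to zero and the effects are in effect dropped. A variance-only test with an exact reference distribution would also hold its level. The plan names neither. Nor should a reader infer inflated false positives: the variance-only test errs on the conservative side.

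On time shape, the plan's lowess plots, diagnostics and segment-linear fallback count in its favour. The shortfall depends on the assumed shape and on time being in months, which the plan does not state. The early difference is also tested directly by the planned t-test of change. On two visits, the extra covariance parameter leaves the arm-by-time estimate and its standard error intact; it is a fitting issue and does not bias the comparison.

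Finally, Section 9.4 describes a hybrid type 3 study, in which clinical outcomes are observed while implementation is tested, and no decision rule hangs on this model. That limits the weight of the point but does not make the specification right.

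**Conclusion.** The point holds for the longitudinal mixed model with random intercepts and slopes, and only there. As written, a two-level arm is a random effect, and the status of the term that tests the group difference is open. The outcome then depends on an unstated choice: an arbitrary standard error (REML with a fixed interaction), the ordinary test by default (ML), or a conservative test that loses 14 to 25 percentage points of power (56% less 42% or 31%). These sizes assume 200 completers per arm, correlation 0.5, time in months and a sustained 0.3 SD effect. The flat REML likelihood does not depend on the effect size.

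The straight-line issue is a secondary design recommendation, conditional on effect shape and time coding. The two sentences on visits for psychological outcomes need to be reconciled. The t-tests of mean change, the adjusted regression, the random-subject and GEE models and the 84.9% in Table 2 stand.

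**What to change.** - In the longitudinal model, enter arm, time and arm-by-time as fixed effects, keep random effects for participant only, and state the estimation method.
- Use categorical visit, or segment-linear time with the knot fixed in advance at the 4th visit. Name the 4th-visit contrast in advance, and report the 6- and 12-month contrasts from the same model.
- State which visits are analysed for the psychological outcomes. If only two are used, an unstructured 2×2 covariance (3 parameters) avoids the surplus parameter.

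The cost is SAP wording. Arm-by-time uses 2 degrees of freedom (one knot) or 3 (categorical visit) instead of 1. If the effect in fact grows linearly to 0.3 SD at 12 months, some power is lost: 85% for the 12-month contrast with categorical visit, or 87% with the knot at the 4th visit, against 92% for the slope test at correlation 0.5.

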Center Portsmouth (NMCP). ADSM who seek care for MSD at NMCP may differ from patients aboard a carrier in terms of type and duration of MSD, rank, deployment status and environment. For example, most of the MSD on the carrier were acute and unlikely to be severe. The NMCP sees all ADSM with MSD regardless of severity and duration. Therefore, we wish to establish feasibility and effectiveness of PiPT in this setting to augment the generalizability of our findings. The results of this study along with those from the carrier study will allow us to modify our rehabilitation strategy to address the needs of specific Navy cohorts across different phases of care in different health care settings. The ultimate goal is to decrease MSD-related chronicity leading to disability in ADSM in support of combat readiness.

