### Treatment

- After signing the consent form, the participant will complete a paper form collecting contact information for follow-up and demographic information. At this point, the participant will be assigned a participant ID number. The researcher will verify the participant's diagnostic code and therapist using AHLTA afterward.
- Before the participant's next PT appointment, the participant will complete the baseline questionnaire battery, a 139 question survey battery. The participant may complete the battery immediately on paper, or at a later date online using a link to REDCap that will be sent via encrypted email. This battery must be completed before their next appointment.
- Participants will receive PT care as prescribed and scheduled by their therapist. Participation in the study will not directly alter their care plan.
  - During Phase II, we anticipate that therapists who completed PiPT training will incorporate the training into their standard care. We will not ask therapists to give differential treatment to patients who are enrolled in the study.
- Participants will complete follow up questionnaire battery after their 4th PT appointment, 6mo and 12mo post enrollment. The first follow-up questionnaire is a 77 question survey battery. The second and third follow-up points use a 68 question battery. All follow-up questionnaires will be completed remotely via REDCap.
- We will collect de-identified SOAP notes from randomly selected participants and review them for verbiage indicating that the therapist employed principles of PiPT. We will collect up to 30 SOAP notes, pertaining to various physical therapists and throughout various stages of treatment.

We chose to conduct this study in sequential cohorts rather than conducting the two cohorts (PiPT and non-PiPT) in parallel because there are no comparable sites with similar characteristics such as type of subjects, catchment area size and availability of the health care team in the Navy.

\*We chose the 4th visit as the first follow-up point for two reasons. First, we expect to see a difference between groups on study outcomes at that point. Secondly, since according to the former head of the NMCP department of physical therapy (PI) the average number of visits at the outpatient PT clinic is 6, the 4th visit will allow us to capture complete data.

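### Section 11.6 tests PiPT as a group-by-time interaction but names no covariate-by-time terms, so as it naturally reads the longitudinal estimate is essentially unadjusted for confounding of change

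*Combined protocol and SAP*

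**What the plan says.** All references are to the combined protocol and SAP.

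- **Design (10.1, Phase II, Treatment).** "We chose to conduct this study in sequential cohorts rather than conducting the two cohorts (PiPT and non-PiPT) in parallel". There is no randomisation.
- **Case mix (9.2).** "The NMCP sees all ADSM with MSD regardless of severity and duration".
- **Adjusted regression (11.6).** After chi-squared tests and t-tests on mean changes, "These univariate analyses will be followed by multivariable regression methods for an adjustment of all other potential confounding variables". The dependent variable of this regression is not given.
- **Longitudinal models (11.6).** "We will also use longitudinal logistic models (i.e., mixed-effects regression models with a random subject effect and GEE with exchangeable and independent correlations"), covering baseline, post-treatment, 6 months and 1 year. Linear mixed models are also planned, and arms are compared on linear trajectories.
- **Random terms (11.6).** Intercepts and slopes are random at two levels, the arm and the individual.
- **Confounders and the test of PiPT (11.6).** "other covariates such as other clinical or demographic confounders will be modeled as fixed effects. An interaction term will be also assessed". The stated purpose of that term is to compare how the two arms change, so it is group by time.

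That is the only interaction named. Section 11.6 refers to the tables in Section 10.2 for the covariates, and those tables give no model form. No analysis is named as primary.

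**The concern.** In the trajectory models the PiPT effect is a difference in change over time. A baseline covariate entered as a main effect explains why some patients are higher or lower throughout. It does not explain why they improve faster. If the two phases recruit different mixes of, say, acute and long-standing disorders, and acute patients recover faster, the interaction picks up the difference in mix. It may then show a PiPT effect that is not there or hide one that is.

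The plan's own background makes this plausible. Section 9.2 reports that high recovery expectations predicted recovery at one year (OR 5.18) and that fear of activity predicted work status at twelve weeks. Aim 2 is to compare baseline risk factors between the cohorts. Time since onset, PCL-M, CES-D and GAD-7 are collected at baseline only, so they are time-invariant covariates. A report could call the slope contrast adjusted for confounders when almost nothing had been adjusted.

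**Working it through.** **1. The plan's own figure.** Table 2 gives 84.9% power for d = 0.3 with 286 per cohort and 30% loss. 286 × 0.7 ≈ 200 completers per cohort. A two-sided t-test at 0.05 (noncentral t) gives 84.9%, so the figure reproduces. I use 200 per cohort in steps 3 and 4.

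**2. Why a main effect changes nothing in the balanced linear case.** Take visits at 0, 1, 6 and 12 months (1 month stands for the post-treatment visit, which 11.6 puts at about 4 weeks). The mean time is 19/4 = 4.75, and the deviations are −4.75, −3.75, 1.25 and 7.25, which sum to 0. Person i's fitted slope is

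s_i = Σ(t_j − 4.75)Y_ij / Σ(t_j − 4.75)²

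Adding γX_i to every visit changes s_i by γX_i × 0 / Σ(t_j − 4.75)² = 0. With complete, balanced data the group-by-time estimate is the difference between the cohorts' mean slopes, so it does not change either.

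**3. Size of the bias.** If s_i = a + bG_i + δX_i + error, the cohort difference in mean slope is b + δ(X̄₁ − X̄₀). The bias is δ × imbalance. Neither factor is given in the documents, so the table shows assumed values. It comes from simulations with no PiPT effect, 200 per cohort and 600 runs per scenario.

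| Share of fast recoverers | Extra improvement over 12 months | Bias | False positives, unadjusted and main-effect models |
|---|---|---|---|
| 50% vs 40% | 0.5 SD | 0.10 × 0.5 = 0.05 SD | 11% |
| 50% vs 40% | 1.0 SD | 0.10 × 1.0 = 0.10 SD | 21% |
| 55% vs 40% | 0.8 SD | 0.15 × 0.8 = 0.12 SD | 24% |
| 55% vs 40% | 1.0 SD | 0.15 × 1.0 = 0.15 SD | 36% |

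With covariate-by-time terms the bias was about 0 and rejection was 3% to 6%. The simulation error of a rate is √(p(1 − p)/600), about 1.3 to 2.0 points for the rates in the table. Hand check of the third row with a standard error of 0.099: 0.12/0.099 = 1.21, 1.96 − 1.21 = 0.75, and P(Z > 0.75) ≈ 23%.

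**4. Many covariates.** With 200 per cohort, 20 covariates and no true effect, the group-by-time estimate was −0.119 without covariates and −0.119 with 20 main effects (largest gap 6 × 10⁻¹⁵, 24% false positives). With covariate-by-time terms it was −0.002 (5.8%). The standard error rose from 0.099 to 0.103, a ratio of 1.04.

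**5. Dropout and logistic models.** Assumed: 300 per cohort, true effect 0, one covariate differing by 0.5 SD between cohorts and changing the slope by −0.5 per SD per year. The expected bias is 0.5 × (−0.5) = −0.25.

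| Analysis | Unadjusted | Main effect | Covariate-by-time |
|---|---|---|---|
| Linear mixed model, complete data | −0.237 | −0.237 | +0.005 |
| Linear mixed model, 30% random dropout | −0.217 | −0.217 | +0.022 |
| Linear mixed model, about 30% dropout depending on the covariate | −0.188 | −0.185 | +0.015 |
| Logistic GEE, independence (log-odds) | 0.368 | 0.388 | −0.029 |

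The largest single-run gap between unadjusted and main-effect estimates was 0.016 in the mixed model and 0.076 under independence. A separate logistic GEE with exchangeable correlation (150 runs, log-odds over 12 months) gave −0.114, −0.121 and 0.007. The table rests on 12 replicates per linear row and 20 for the logistic row. It shows whether the models agree, not how often they reject.

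**6. The other planned route.** In the complete-data setting of step 5, regressing change on group gave −0.250. Adding the covariate gave −0.010.

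**The case against.** Four points can be made for the plan, and each limits what may be concluded.

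- **Main effects only.** A reader might infer that the plan restricts covariates to main effects. It does not say so. Fixed is set against random in that sentence, and a covariate-by-time term is also a fixed effect. The text is silent on such terms. Still, it names one interaction and no other, and an analyst following it would fit main effects.
- **No adjustment of recovery anywhere.** This stronger reading also fails. The longitudinal models come in addition to a multivariable regression that follows t-tests on change. Step 6 shows that such a regression removes the bias if change is its outcome. For psychological outcomes, 11.6 in one place limits the analysis to baseline and post-treatment, where an adjusted change regression does the whole job; elsewhere it plans their trajectories. What remains is that the regression's outcome is not stated.
- **Adjusted equals unadjusted, always.** Exact equality needs a linear model, time-invariant covariates and complete balanced data. Roughly 30% attrition is planned (11.5), logistic models are named, and Section 10.2 lists duty status and mental health care as confounders measured at every visit. Multiple imputation restores balance within each imputed set, but otherwise equality is only approximate. Step 5 shows that the bias stays. Follow-up values of duty status would not stand in for baseline factors such as time since onset.
- **Size.** No imbalance or recovery difference comes from the documents. One might also infer that power falls from 84.9% to about 51% if 0.1 SD of confounding offsets a true 0.3 SD effect. That is t-test power at 0.2 SD under an assumed bias, not the power of the longitudinal interaction, and the t-test is followed by an adjusted regression.

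**Conclusion.** The point holds as a fault of specification that has a predictable consequence. Fitted as 11.6 naturally reads, the group-by-time estimate is essentially unadjusted for confounding of change, in a design where that confounding is the main threat. In the assumed scenarios the bias is 0.05 to 0.15 SD, with 11% to 36% false positives at 200 per cohort. It is zero if the cohorts are balanced on the covariate or if the covariate does not affect the slope. The algebra in step 2 does not depend on those assumptions; the sizes do. The documents do not show that covariate-by-time terms are excluded or that every planned analysis is unadjusted. The correction deals with measured confounders only. Other changes between the two phases remain a limit of the sequential design.

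**What to change.** In Section 11.6, replace the sentence on fixed effects with wording to this effect:

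- Each prespecified baseline confounder (listed by name from Section 10.2) enters the mixed and GEE models as a main effect and as a covariate-by-time interaction, using the same form of time, linear or segmented, as the group-by-time term.
- The PiPT effect is the group-by-time contrast from that model.
- The separate multivariable regression uses change, or follow-up adjusted for the baseline value, as its outcome.
- One adjusted estimate is named as primary.

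An alternative to the first item is to regress follow-up values on group, baseline value and covariates, with visit-specific coefficients. The imputation model should hold the same covariates and the outcome at each visit, so that imputed values keep the covariate-by-time relation.

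The cost is a few sentences and additional parameters. No new data are needed. The standard error rose by about 4% with 20 covariates (0.099 to 0.103) and hardly at all with one (0.097 against 0.097 to 0.098).
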